## OS:

The duration of OS is defined as the time from randomization to death from any cause. OS will be analyzed as for rPFS.

The O'Brien-Fleming alpha spending function will be used to determine the stopping boundaries based on the number of events observed at the interim look to control the overall 2-sided alpha at 0.05 or at 0.04 (as described in Figure 2).

EudraCT number 2015-003869-28

- CONFIDENTIAL -

The interim analysis of OS expected at the time of the final analysis of rPFS will be performed at an expected significance level of 0.006 based on approximately 170 death events. If this interim analysis of OS is not statistically significant, the final analysis of OS is planned when approximately 342 deaths are observed to ensure an adequate number of events for the evaluation of OS.

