Time to event endpoints such as rPFS, time to PSA progression, OS, time to first SSE, time to castration resistance, time to deterioration of QoL, time to deterioration in urinary symptoms, time to pain progression and time to initiation of new antineoplastic therapy will be analyzed using the stratified log-rank test. The stratified Cox Regression analysis will be used to estimate the HR and the associated 95% CI. The median will be estimated using the Kaplan-Meier method.

One interim analysis and the final analysis are planned for OS. The interim analysis of OS will be performed at the time of the rPFS final analysis. The significance level will be determined by the O'Brien-Fleming alpha spending function based on the number of events observed at the interim look. The final analysis of OS will be conducted when approximately 342 deaths are observed to ensure an adequate number of events for the evaluation of OS.

The proportion endpoints such as PSA undetectable rate and ORR will be analyzed using the stratified Cochran-Mantel-Haenszel score test.

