# 7.1 Sample Size

As originally planned, approximately 1100 subjects (550 subjects per treatment arm) will be randomized in the study.

The final analysis of rPFS will be conducted with a minimum of 262 progression events based on the following considerations:

- A target HR is 0.67. The expected median rPFS for the ADT arm is 20 months as measured from the date of randomization. A target HR of 0.67 corresponds to approximately 50% increase in median rPFS for the enzalutamide plus ADT arm relative to the placebo plus ADT arm (approximately 30 versus 20 months).
- The required minimum of 262 rPFS events (radiographic progression or death on study, defined as death from any cause within 24 weeks after treatment discontinuation, whichever occurs first) provides 90% power to detect a target HR of 0.67 based on a 2-sided log-rank test and significance level of 0.05.

Additionally the study is powered for OS. Specifically, 342 death events will be required to provide 80% power to detect a target hazard ration of 0.73 with a target difference in Kaplan-Meier estimated median of approximately 15 months (40 months for placebo versus 55 months for enzalutamide) at the 4% significance level. This significance level was chosen to apply a parallel testing strategy between OS and some other secondary endpoints (with allocated type I error rate of 1%) as described in Section 7.4.2.

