### 7.4.2 Analysis of Secondary Endpoints

All secondary endpoint analyses will be performed at the time of the rPFS final analysis.

The following 6 secondary endpoints will be tested: OS, time to PSA progression (TTPSA), time to initiation of a new antineoplastic therapy (TTNAnti), the rate of PSA decline to < 0.2ng/mL (PSADecR), the objective response rate (ORR) and time to deterioration in urinary symptoms (TTUri). A parallel testing strategy between OS (with allocated type I error rate 0.04) and the other 5 endpoints (with allocated type I error rate 0.01) will be performed, as summarized in Figure 2.

- CONFIDENTIAL -

Figure 2 Testing Strategy for the Primary and 6 Selected Secondary Endpoints

OS: overall survival; ORR: objective response rate; PSADecR: rate of PSA decline to < 0.2 ng/mL; rPFS: radiographic progression-free survival; TTNAnti: time to initiation of a new antineoplastic therapy; TTPSA: time to PSA progression; TTUri: time to deterioration in urinary symptoms from the QLQ-PR25. \*OS will be tested at 0.05 only if the other 5 secondary endpoints analyses are statistically significant at 0.01.

Details of the primary and the selected secondary endpoints testing as a step-by-step approach will be described in the Statistical Analysis Plan (SAP).

One interim analysis and a final analysis are planned for OS. The interim analysis of OS will be performed at the time of the rPFS final analysis. If this interim analysis of OS is statistically significant, it will be reported as the final analysis and no subsequent analysis will be performed. At the time of the planned final analysis of OS, no additional analyses of other efficacy endpoints will be conducted.

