#### 7.4.1 Overall Survival

At the time of the primary analysis of rPFS, the interim analysis of OS was not significant (84 deaths from any cause, 39 in Enzalutamide + ADT group and 45 in Placebo + ADT group, p=0.3361 from stratified log-rank test). The final analysis of OS will be conducted when approximately 342 events (death from any cause) have occurred.

At the time of the primary analysis of rPFS, the following six key secondary endpoints were tested: OS, Time to PSA progression, time to initiation of a new antineoplastic therapy, the rate of PSA decline to <0.2ng/mL (PSADecR), objective response rate and the time to deterioration in urinary symptoms from the QLQ-PR25. To maintain the family-wise 2-sided type I error rate at 0.05, a parallel testing strategy between OS (with allocated type I error rate 0.04) and the other five endpoints (with allocated type I error rate 0.01) was performed, as summarized in Figure 1.

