#### Figure 1 Testing Strategy for the Primary and Six Selected Secondary Endpoints

rPFS: radiographic progression-free survival; OS: overall survival; TTPP: time to PSA progression; TTNAnti: time to initiation of a new antineoplastic therapy; PSADecR: rate of PSA decline to <0.2 ng/mL; ORR: objective response rate; TTUri: the time to deterioration in urinary symptoms from the QLQ-PR25 \*OS will be tested at 0.05 only, if all other 5 secondary endpoints analyses are statistically significant at 0.01.

As the analysis for time to deterioration in urinary symptoms from the QLQ-PR25 was not significant, the final analysis of OS will be conducted at the level of significance of 0.04 (2-sided). The effect of Enzalutamide+ADT compared to placebo+ADT will be tested using a log-rank test stratified by prior docetaxel use (yes versus no) and disease volume (low versus high).

The null and alternative hypotheses to be tested are as follows:

The null hypothesis: OS for Placebo+ADT and Enzalutamide+ADT are not different The alternative hypothesis: OS for Placebo+ADT and Enzalutamide+ADT are different

The following SAS code will be used to compute the Kaplan-Meier estimates and curves, and the stratified log-rank test:

PROC LIFETEST DATA=INPUT ATRISK

```
PLOTS=SURVIVAL(CB)
OUTSURV=SURVPL
ALPHA=0.04
ALPHAQT=0.04 METHOD=KM;
TIME AVAL*CNSR(1);
STRATA STRATUM/ GROUP=TREATMENT;
RUN;
where INPUT is the input dataset
```

AVAL is the time to the event variable,

CNSR is 0 (patients with events) or 1 (patients without no event, i.e. patient censored) STRATUM is the stratification variable (volume of disease and prior docetaxel use) TREATMENT is the treatment variable

Kaplan-Meier methods will be used to estimate the distribution of OS events by treatment group. The median OS will be estimated using the corresponding 50th percentile of Kaplan-Meier estimates. A two-sided 95% confidence interval will be provided for this estimate by use of the Brookmeyer and Crowley method. The 25th percentile and the 75th percentile of OS will also be provided. A Kaplan-Meier plot by treatment group will be presented. The estimates of the event free rate on a 3-monthly basis up to 1 year and every 6 months thereafter will be summarized by treatment group, as long as at least 10 patients are at risk.

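### Is the expected OS interim level of 0.006 in Protocol 7.4.2 wrong for the 0.04 allocated to OS?

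*Protocol*

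**What the plan says.** Protocol 7.4.2 splits the secondary alpha: 0.04 to OS and 0.01 to five other endpoints. The footnote to Figure 2 adds that "OS will be tested at 0.05 only if the other 5 secondary endpoints analyses are statistically significant at 0.01".

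Under the OS heading of the same section, an O'Brien-Fleming alpha spending function is used "to control the overall 2-sided alpha at 0.05 or at 0.04 (as described in Figure 2"). The next paragraph gives a single expected level: the interim is to be "performed at an expected significance level of 0.006 based on approximately 170 death events". If that look is not significant, the final analysis follows at about 342 deaths.

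Two other places bear on the reading:

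- The Synopsis (Statistical Methods) says the level comes from the O'Brien-Fleming "alpha spending function based on the number of events observed at the interim look".
- Protocol 7.1 states that "342 death events will be required to provide 80% power to detect a target hazard ration of 0.73", and does so "at the 4% significance level. This significance level was chosen to apply a parallel testing strategy between OS and some other secondary endpoints".

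SAP 7.4.1 reports the interim as done and not significant ("84 deaths from any cause, 39 in Enzalutamide + ADT group and 45 in Placebo + ADT group, p=0.3361"). Because the urinary-symptom endpoint was not significant, it states that "the final analysis of OS will be conducted at the level of significance of 0.04".

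**The concern.** Two different overall alphas cannot share one interim level at the same information fraction, yet only one level is printed. A reader would naturally attach it to the 0.04 that OS is guaranteed, particularly as the 342 deaths are sized at 4%. On that reading 0.006 is too generous: the 0.04 level at 170 deaths is about 0.0036, so the printed value is about 1.7 times as large. In terms of the observed hazard ratio needed to stop at 170 deaths, this is 0.656 rather than 0.640.

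What would be at stake is type I error control for OS. If 0.006 were applied at the interim and the final test kept the level that goes with 0.0036, the overall two-sided error would exceed the 0.04 allocated.

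**Working it through.** **Inputs.** Interim at about 170 deaths and final at about 342 (Protocol 7.4.2, OS); overall two-sided alpha 0.04 or 0.05 (same place); target HR 0.73 and 80% power (Protocol 7.1); 1:1 randomization (Protocol 2.2.1); actual interim at 84 deaths (SAP 7.4.1).

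**Assumed form.** The documents name the spending function but give no formula. Applied to the total two-sided alpha, the interim level is

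p(t) = 2 × [1 − Φ(z(1−α/2) / √t)], with t = deaths/342.

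**Reproducing the printed 0.006.** With α = 0.05, z = 1.960:

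- 170 deaths: t = 0.4971, √t = 0.7050, 1.960/0.7050 = 2.780, level 0.0054.
- 171 deaths: t = 0.5, √t = 0.7071, 1.960/0.7071 = 2.772, level 0.0056, which rounds to 0.006.
- 174 deaths: level 0.0060.

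The level reaches 0.0055, and so rounds to 0.006, from about 170.5 deaths. At half of the planned information the 0.05 alpha reproduces the printed value at its precision.

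**The same calculation for α = 0.04**, z = 2.054:

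- 170 deaths: 2.054/0.7050 = 2.913, level 0.0036.
- 171 deaths: 2.054/0.7071 = 2.904, level 0.0037.

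Reaching 0.0055 would take about 187 deaths and 0.006 about 191, which is more than the word approximately can cover.

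**Other conventions at 170 of 342 deaths:**

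| Convention | α = 0.04 | α = 0.05 |
|---|---|---|
| Spending on total two-sided alpha | 0.0036 | 0.0054 |
| Classic O'Brien-Fleming boundary | 0.0034 | 0.0050 |
| Spending per tail | 0.0019 | 0.0030 |

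None gives 0.006 for α = 0.04. Only the first, with α = 0.05, comes close enough to explain the printed figure.

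**The misuse case.** In a two-look design at t = 170/342 (correlation √t between looks), an overall alpha of 0.04 with interim level 0.0036 has a final level of 0.0386. Using 0.006 at the interim and keeping 0.0386 gives an overall two-sided error of 0.0413, an excess of 0.0013. If 0.006 had been spent and overall alpha held at 0.04, as the plan requires, the final level would fall to 0.0372 and there would be no excess.

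**What happened.** At 84 deaths, t = 84/342 = 0.2456 and √t = 0.4956:

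- α = 0.05: 1.960/0.4956 = 3.955, level 0.000077.
- α = 0.04: 2.054/0.4956 = 4.144, level 0.000034.

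The observed p was 0.3361. At most 0.000034 of the 0.04 was spent, so the final test has at least 0.04 − 0.000034 = 0.03997 left, which is 0.04 at the precision the SAP states.

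**The case for a change.** The best case for a change is that the sentence is incomplete on its face, that 0.006 is the only numeric OS interim threshold in the readable text, and that it does not suit the 0.04 alpha, which turned out to be the one in force. The same paragraph quotes 342 deaths, and Schoenfeld's formula ties that count to 4%: 4 × (2.054 + 0.842)² / (ln 0.73)² is about 339 deaths at 0.04, against 317 at 0.05. The paragraph thus seems to pair an interim level from one alpha with an event count from the other. A label would cost one sentence.

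The missing label stands. The rest does not carry far. Sizing the final count at the smaller, guaranteed alpha is ordinary prudence, and it does not prevent an author from quoting the expected interim level for the larger one. Since the section allows both alphas, there is no contradiction. The 0.0413 case needs someone to skip the calculation from observed deaths, put a planning value under the wrong alpha, and keep a final level derived for a different interim. Each of these departs from the plan.

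The obvious rewording also has a weakness. Printing 0.0036 and 0.0054 would write an assumed spending form into the protocol, while the conventions tried run from 0.0019 to 0.0036 for alpha 0.04.

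**Conclusion.** No change is needed. The 0.006 is an unlabelled planning value, correct to its one printed digit for an overall alpha of 0.05 at half of 342 deaths. It is not the level for 0.04, which is about 0.0036 under the same form, but nothing in the text says that it is.

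The operative rule is sound: the boundary comes from the spending function at the observed number of deaths, with overall alpha held at 0.04 or 0.05. An analyst who follows it gets a valid interim test under either alpha. The sentence also describes an analysis that is over. The SAP of 18 July 2021 reports the interim at 84 deaths, the protocol version reviewed is dated 18 April 2022, and the final level is settled at 0.04. A label would alter no boundary, event count or conclusion.

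This rests on two assumptions. The first is that spending was on the total two-sided alpha; linking 0.006 to the 0.05 alpha is an inference from a one-digit figure. The second is that nothing in the graphics of Protocol Figure 2 and SAP Figure 1, or in the main study SAP (version 3.0), none of which was available, conflicts with this reading. Neither affects the outcome of the interim: under every convention tried, the boundary at 84 deaths is below 0.0001.

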### Time to first SSE:

Time to first SSE is defined as the time from randomization to the occurrence of the first SSE. SSE is defined as radiation or surgery to bone, clinically apparent pathological bone fracture or spinal cord compression. The analysis method will be the same as for rPFS.

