#### **Concomitant Medication Restrictions or Requirements:**

Required Concomitant Treatment

All subjects will be required to maintain ADT during study treatment, either using an LHRH agonist/antagonist or having a history of bilateral orchiectomy.

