## Secondary Endpoints

- OS: Defined as the time from randomization to death from any cause.
- *Time to first SSE:* Defined as the time from randomization to the occurrence of the first SSE. SSE is defined as radiation or surgery to bone, clinically apparent pathological bone fracture or spinal cord compression.
- *Time to castration resistance:* Defined as the time from randomization to the first castration-resistant event (radiographic disease progression, PSA progression or SSE), whichever occurs first.
- *Time to deterioration of QoL*: Defined as time from randomization to a 10-point reduction of the FACT-P total score.
- *Time to deterioration in urinary symptoms:* Defined as time from randomization to an increase of ≥ 50% of the standard deviation at baseline in the modified urinary symptoms score of QoL PR25.
- *Time to initiation of a new antineoplastic therapy:* Defined as the time from randomization to the initiation of antineoplastic subsequent to the study treatments.
- *Time to PSA progression:* Defined as the time from randomization to PSA progression, which is a ≥ 25% increase and an absolute increase of ≥ 2 μg/L (2 ng/mL) above the nadir (i.e., lowest PSA value observed post baseline or at baseline), which is confirmed by a second consecutive value at least 3 weeks later.
- *PSA undetectable rate*: Defined as percentage of subjects with detectable (≥ 0.2 ng/mL) PSA at baseline which become undetectable (< 0.2 ng/mL) during study treatment.
- *ORR*: Defined as the percentage of subjects with measureable disease at baseline who achieved a complete or partial response in their soft tissue disease using the RECIST version 1.1 criteria.
- Time to pain progression: Defined as time from randomization to an increase of  $\geq$  30% in pain severity score from baseline using the BPI-SF.

All secondary endpoint analyses will be performed at the time of the rPFS primary analysis.

Six secondary endpoints (OS, time to PSA progression, time to initiation of a new antineoplastic therapy, the rate of PSA decline to < 0.2 ng/mL, ORR and time to deterioration in urinary symptoms) will be tested utilizing a parallel testing strategy. The methodology used will be described in detail in the statistical analysis plan.

EudraCT number 2015-003869-28

- CONFIDENTIAL -

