# 1.3 Summary of Key Safety Information for Study Drugs

Enzalutamide has been approved by the FDA, the EMA and Japan MHLW for metastatic CRPC. Worldwide, enzalutamide has been approved for the treatment of metastatic CRPC in more than 100 countries. Enzalutamide has also been approved for nonmetastatic CRPC in the US, EU and Japan as well as in more than 60 countries. In Dec 2019, enzalutamide was approved for the treatment of metastatic CSPC in the US (also referred to as mHSPC) and a marketing application for this indication is currently in review in the EU.

The safety profile of enzalutamide in subjects with CRPC is derived primarily from 5 phase 3 studies. Study CRPC2 (AFFIRM) was a randomized, double-blind, placebo-controlled, efficacy and safety clinical study of enzalutamide (160 mg daily) in 1199 subjects with progressive metastatic CRPC (mCRPC) previously treated with docetaxel-based chemotherapy. Study MDV3100-03 (PREVAIL) was a multinational, randomized, double-blind, placebo-controlled, efficacy and safety clinical study of enzalutamide in 1717 chemotherapy naïve subjects with mCRPC who have failed ADT. Study 9785-CL-0232 (Asian PREVAIL) was similar to PREVAIL except in an Asian population of 388 subjects. Study MDV3100-14 (PROSPER) was a randomized, double-blind, placebo-controlled, efficacy and safety clinical study of enzalutamide (160 mg daily) in 1401 subjects with nonmetastatic CRPC at high risk of disease progression based on baseline prostate-specific antigen (PSA) level and short PSA doubling time.

An analysis of 5 pooled phase 3 studies (AFFIRM, PREVAIL, Asian PREVAIL, PROSPER and ARCHES) indicated that the most frequently reported treatment-emergent adverse events (TEAEs) reported in  $\geq 10\%$  of patients in the enzalutamide group (n = 3371; enzalutamide dose; 160 mg/day) were:fatigue, back pain, nausea, hot flush, constipation, arthralgia, decreased appetite, diarrhea, hypertension, asthenia, fall, pain in extremity, musculoskeletal pain and headache. With the exception of nausea and pain in extremity, each of these events occurred in the pooled phase 3 enzalutamide group with a  $\geq 2\%$  higher incidence than in the placebo group (n = 2472). Only 2 TEAEs showed a higher rate in the enzalutamide vs the placebo group (event rate per 100 patient-years of treatment): fall (8.9% enzalutamide vs 4.6% placebo) and hypertension (8.2% vs 5.5%).

- CONFIDENTIAL -

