When adjusted for treatment duration, the event rates for grade  $\geq$  3 TEAEs showed small differences ( $\leq$  1.2 events per 100 patient years) between the enzalutamide group and the placebo group.

Study drug-related TEAEs reported in  $\geq$  5% of patients in the enzalutamide group were fatigue (24.1% enzalutamide vs 14.1% placebo), hot flush (14.0% vs 8.7%), nausea (11.7% vs 10.4%), decreased appetite (8.2% vs 5.5%), asthenia (7.4% vs 4.4%), diarrhea (5.6% vs 4.4%) and hypertension (5.6% vs 2.0%).

The incidence of TEAEs leading to death was low in the pooled enzalutamide groups (4.8%) and in the placebo group (2.8%) and the adjusted event rates for serious TEAEs were also comparable in both groups.

The incidence of TEAEs leading to permanent discontinuation of study drug was similar in both groups; 17.2% in the pooled enzalutamide groups and 16.1% in the placebo group. The incidence of TEAEs leading to a dose reduction was 5.6% in the phase 3 enzalutamide group and 2.0% in the phase 3 placebo group. The incidence of TEAEs leading to a dosing interruption was 15.0% in the phase 3 enzalutamide group and 9.9% in the phase 3 placebo group

The pooled phase 3 safety data confirms that convulsion/seizure, cognitive and memory impairment, fatigue-related events, neutropenia/neutrophil count decreased, fall, fracture and hypertension are adverse events of special interest (AESI) for enzalutamide. Posterior reversible encephalopathy syndrome (PRES) is also considered an AESI for enzalutamide; however, this is based on cases reported during postapproval use of enzalutamide and not on events occurring in clinical studies.

Severe cutaneous adverse reactions, including acute generalized exanthematous pustulosis, dermatitis bullous, dermatitis exfoliative generalized, drug reaction with eosinophilia and systemic symptoms, erythema multiforme, exfoliative rash, Stevens-Johnson syndrome, toxic epidermal necrolysis and toxic skin eruption have been reported in post-marketing cases.

For more information on the investigational product enzalutamide and on the clinical study experience, refer to the current Investigator's Brochure of enzalutamide.

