Lastly, the primary efficacy analysis in ARCHES demonstrated a statistically significant, robust and substantial improvement in radiographic progression-free survival together with clinically meaningful improvements in the key secondary endpoints of time to PSA progression, time to start of a new antineoplastic therapy, PSA undetectable rate and objective response rate and a trend in OS (observed at the time of interim analysis) in favor of enzalutamide plus ADT versus placebo plus ADT treatment. For the secondary endpoints, the ARCHES study demonstrated that enzalutamide prolonged the time to the first symptomatic skeletal event and time to castration-resistance. Assessments of patient-reported outcomes data showed that patients receiving enzalutamide plus ADT in ARCHES had a high baseline level of quality of life, which was maintained over time.

Based on the safety information collected to date in clinical trials and in commercial use, the safety profile experienced by patients remains consistent with the approved product label as well as events that can be seen in patients with prostate cancer. The safety profile in mHSPC patients in this study is expected to be consistent with the established safety profile for enzalutamide. To date, there are 4 important identified risks associated with enzalutamide (seizure, fall, nonpathological fracture and ischemic heart disease). While serious adverse events (SAEs) such as seizure have occurred in patients receiving treatment with enzalutamide, these events have been rare. To mitigate the risk of seizure, subjects with a history of seizure or any condition that may predispose to seizure (e.g., prior cortical stroke or significant brain trauma, brain arteriovenous malformation) are excluded from the trial. Study drug discontinuation is required for subjects experiencing either seizure or PRES. In addition to these patient exclusion and discontinuation requirements, the study design includes safety labs, scans and guidance related to concomitant medications to minimize the risks associated with enzalutamide and ensure timely intervention if needed.

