## Time to castration resistance:

Castration resistance is defined as occurrence of radiographic disease progression, PSA progression or SSE with castrate levels of testosterone (< 50 ng/dL). Time to castration resistance is defined as the time from randomization to the first castration-resistant event (radiographic disease progression, PSA progression or SSE), whichever occurs first. The analysis method will be the same as for rPFS.

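### The SSE definition attaches no cancer indication to bone surgery or radiation, so repair of a nonpathological fracture counts as an SSE and, at castrate testosterone, as castration resistance

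*Protocol*

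**What the plan says.** Protocol Section 7.4.2 (Time to first SSE) and the Synopsis define the event in the same words: "SSE is defined as radiation or surgery to bone, clinically apparent pathological bone fracture or spinal cord compression". The adjective pathological governs the fracture component only. Neither the protocol nor the supplied SAP attaches an indication to the procedure component or gives an adjudication rule for it.

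SSE then feeds a second endpoint. Section 7.4.2 (Time to castration resistance) counts "radiographic disease progression, PSA progression or SSE with castrate levels of testosterone", with the threshold at 50 ng/dL. The Synopsis describes the "first castration-resistant event (radiographic disease progression, PSA progression or SSE), whichever occurs first" and does not repeat the testosterone condition. The Synopsis also says "All subjects will be required to maintain ADT during study treatment", so a subject on treatment will usually meet that condition.

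On safety, Section 1.4 says "there are 4 important identified risks associated with enzalutamide (seizure, fall, nonpathological fracture and ischemic heart disease". Section 1.3 says that "fall, fracture and hypertension are adverse events of special interest (AESI) for enzalutamide", and gives pooled event rates per 100 patient-years that include "fall (8.9% enzalutamide vs 4.6% placebo".

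**The concern.** The definition lets back in what it has just excluded. A subject who falls, breaks a hip through trauma and has it fixed has no pathological fracture, so the fracture component is not met. The operation is nevertheless surgery on bone, so the procedure component is met. If his testosterone is castrate, the same operation is also a castration-resistance event, even with falling PSA and stable scans.

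The miscounting need not be balanced between arms. The protocol's own safety text gives reason to expect more falls and nonpathological fractures on enzalutamide. A possible harm of the drug would then be scored as disease progression in time to first SSE and time to castration resistance. The estimated benefit would shrink, and neither endpoint would measure quite what its name says. Section 1.4 cites both endpoints in support of the risk-benefit assessment, so their meaning matters even though neither is formally tested within the alpha-controlled family.

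**Working it through.** **Text check.** There is no plan figure to reproduce: the documents give no event count, power or alpha for either endpoint. Applying the written rule to three cases:

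- Nonpathological fracture managed without surgery: not an SSE.
- Nonpathological fracture repaired surgically: an SSE through the procedure component.
- The same repair with testosterone below 50 ng/dL: also castration resistance under Section 7.4.2. Under the Synopsis wording it counts without a testosterone condition.

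**Illustration of size.** Inputs:

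- True cancer-related SSE hazard ratio 0.72. This is the skeletal-related-event result in chemotherapy-naïve metastatic castration-resistant disease quoted in Protocol Section 1.4, borrowed here as an assumption.
- Placebo cancer-related SSE rate p = 6 per 100 patient-years, range 4 to 10. Assumed; not in the documents.
- Placebo rate of non-cancer bone surgery s = 0.2 to 0.5 per 100 patient-years. Assumed; not in the documents.
- Rate ratio R for that surgery, enzalutamide to placebo: from 1.0 (no drug effect) to 8.9/4.6 = 1.93, the fall ratio from Section 1.3 used as a proxy.

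With constant rates that add within each arm, placebo has p + s and enzalutamide has 0.72p + R·s, so

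observed HR = (0.72p + R·s) / (p + s).

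For p = 6:

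- R = 1.0, s = 0.2: (4.32 + 0.20)/6.2 = 0.729
- R = 1.0, s = 0.5: (4.32 + 0.50)/6.5 = 0.742
- R = 1.93, s = 0.2: (4.32 + 0.387)/6.2 = 0.759
- R = 1.93, s = 0.5: (4.32 + 0.967)/6.5 = 0.813

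Over the range of p:

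| p | s | Share of placebo events, s/(p+s) | HR if R = 1.0 | HR if R = 1.93 |
|---|---|---|---|---|
| 4 | 0.2 | 4.8% | 0.733 | 0.778 |
| 4 | 0.5 | 11.1% | 0.751 | 0.855 |
| 6 | 0.2 | 3.2% | 0.729 | 0.759 |
| 6 | 0.5 | 7.7% | 0.742 | 0.813 |
| 10 | 0.2 | 2.0% | 0.725 | 0.744 |
| 10 | 0.5 | 4.8% | 0.733 | 0.778 |

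The formula moves the hazard ratio upward whenever R exceeds 0.72. An excess on enzalutamide is therefore not needed for dilution, but it makes the dilution larger. No corresponding figure is given for castration resistance. Radiographic and PSA progression also contribute events there, so the share of miscounted events, and hence the shift, should be smaller.

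**The case against.** **The operative definition may lie elsewhere.** SAP Section 6 says that variables are defined in the SAP for the primary analysis, which SAP Section 1 identifies as version 3.0. Neither that document nor the CRF was available, and an indication field or derivation rule could sit in either. This stands. It limits the point to the protocol wording and leaves open how events were actually classified.

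**Context suggests cancer-related procedures.** Protocol Section 5.1.3.4 permits palliative radiation, and palliative surgery for skeletal-related events. Section 12.6.2 collects skeletal-related events together with their interventions. This makes the intended meaning fairly clear, and counting an elective joint replacement would be a strained reading. It does not change what the definition literally admits.

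**The consequence is limited.** Neither endpoint is among the six alpha-controlled secondary endpoints in Section 7.4.2, and neither affects rPFS, OS or the sample size. The shift runs against enzalutamide. Fractures and falls are also summarised separately as events of special interest (SAP Section 7.5.1, Table 3), so the harm signal is not lost. All of this stands.

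**The size is largely assumed.** The fall ratio comes from event rates, in which repeat falls may count. It is not a hazard ratio for surgically repaired fractures, and it has no stated relevance to other non-cancer bone surgery. The documents also offer no drug-related route for the radiation part of the component. This stands, which is why R = 1.0 is shown alongside 1.93.

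**It is late to redefine the endpoint.** Section 7.4.2 ties the secondary analyses to the rPFS final analysis and plans no further analysis of other efficacy endpoints at the final OS analysis. Section 1.4 reports results for both endpoints, and Section 12.6.1 describes unblinding at the end of the double-blind period. Changing the main definition now would be a post hoc change in the drug's favour. This stands and shapes the fix.

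**Conclusion.** The point holds on the protocol's wording. The procedure component has no cancer indication, so surgical repair of a nonpathological fracture meets the SSE definition and, at testosterone below 50 ng/dL, the castration-resistance definition. The likely effect is dilution of the apparent enzalutamide benefit on two secondary endpoints outside the alpha-controlled family, with castration resistance affected less.

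The size cannot be derived from the documents. With p = 6, s = 0.2 to 0.5 and a true hazard ratio of 0.72, the result is 0.73 to 0.74 if non-cancer bone surgery is equally common in both arms. It is 0.76 to 0.81 if the fall ratio applies. Every one of those inputs is an assumption for this trial.

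A reader might infer that the reported SSE and castration-resistance results are materially biased, or that an efficacy claim is unsafe. The documents support neither. They do not show that any such procedure was counted, the unavailable SAP version 3.0 or CRF may already exclude them, and an excess of such surgery on enzalutamide would understate the benefit, not inflate it.

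**What to change.** In Protocol Section 7.4.2 and the Synopsis, state that the procedure component means radiation or surgery to bone for a prostate cancer bone metastasis or a pathological fracture. Leave the other two components unchanged. Carry the same restricted SSE into time to castration resistance, and state the testosterone condition in both places.

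Then check SAP version 3.0 and the CRF:

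- If the reported analysis already applied this restriction, only the protocol text needs aligning.
- If it did not, keep the reported analysis as it is. Add a clearly labelled post hoc sensitivity analysis of both endpoints that excludes procedures for nonpathological fracture or other non-cancer indications. Classify each procedure by its recorded indication, using reviewers masked to treatment arm. Justify the addition in the clinical study report.

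The cost is slightly fewer events, some review of bone-procedure records, and the limited weight that a post hoc analysis carries.
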